2.0 STUDY OBJECTIVES

2.1 Primary Objective:

To evaluate whether genomic based risk-stratification can be used in deciding whether to de-intensify in patients with HPV-associated OPSCC with > 10 pack years smoking history. Hypothesis: Patients with HPV-associated OPSCC, > 10 pack years smoking history, and non-mutated p53 will have similar 2 year PFS as patients with < 10 pack years smoking history.

2.2 Secondary Objectives

To prospectively assess if the changes in plasma circulating free HPV DNA during and after treatment are associated with clinical outcomes in patients with HPV-associated OPSCC. Hypothesis: Changes in levels of plasma circulating free HPV DNA during and after treatment will correlate with cancer control rates.

To assess the 2 year clinical outcomes of local control (LC), regional control (RC), local-regional control (LRC), distant metastasis free survival (DMFS), and overall survival (OS).

3.0 ENDPOINTS

3.1 Primary Endpoint

Patients with HPV-positive and/or p16-positive OPSCC will receive de-intensified CRT. The 2 year PFS will be evaluated. Our null hypothesis (H_0) is that the PFS rate is 93% and our alternate hypothesis (H_1) is that the PFS rate is 86%.

3.2 Secondary Endpoints

Circulating free HPV-DNA: Kinetic of cfHPV-DNA copy numbers during and after treatment.

Clinical Outcomes: Kaplan Meier estimates of LC, RC, LRC, DMFS, and OS will be calculated.

4.0 PATIENT ELIGIBILITY

4.1 Inclusion Criteria

- 4.1.1** ≥ 18 years of age (no upper age limit)
- 4.1.2** T0-3, N0 to N2c, M0 squamous cell carcinoma of the oropharynx (AJCC 7th edition)
- 4.1.3** Biopsy proven squamous cell carcinoma that is HPV and/or p16 positive
- 4.1.4** Radiologic confirmation of the absence of hematogenous metastasis within 12 weeks prior to treatment; at a minimum, chest x-ray is required. CT imaging of the chest or PET/CT is acceptable.
- 4.1.5** ECOG Performance Status 0-1
- 4.1.6** CBC/differential obtained within 8 weeks prior to treatment, with adequate bone marrow function defined as follows:
 - 4.1.6.1** Platelets $\geq 100,000$ cells/mm³
 - 4.1.6.2** Hemoglobin ≥ 8.0 g/dl (Note: The use of transfusion or other intervention to achieve Hgb ≥ 8.0 g/dl is acceptable.)
- 4.1.7** Adequate renal and hepatic function within 4 weeks prior to treatment, defined as follows:
 - 4.1.7.1** Serum creatinine < 2.0 mg/dl
 - 4.1.7.2** Total bilirubin $< 2 \times$ the institutional ULN

4.1.7.3 AST or ALT < 3 x the institutional ULN.

Note that physician attestation of patient having no known history of liver disease can take the place of bilirubin and AST/ALT labs.

- 4.1.8** Negative pregnancy test within 2 weeks prior to treatment for women of childbearing potential
- 4.1.9** Women of childbearing potential and male participants who are sexually active must practice adequate contraception during treatment and for 6 weeks following treatment.
- 4.1.10** Patients must be deemed able to comply with the treatment plan and follow-up schedule.
- 4.1.11** Patients must provide study specific informed consent prior to study entry

4.2 Exclusion Criteria

- 4.2.1** Prior history of radiation therapy to the head and neck
- 4.2.2** Prior history of head and neck cancer.
- 4.2.3** Unresectable disease (e.g. immobile node on physical exam, nodal disease that radiographgically involves the carotid arteries, nerves)
- 4.2.4** Currently taking Disease Modifying Rheumatoid Drugs (DMRDs)
- 4.2.5** Severe, active co-morbidity, defined as follows:
 - 4.2.5.1** Unstable angina and/or congestive heart failure requiring hospitalization within the last 6 months
 - 4.2.5.2** Transmural myocardial infarction within the last 6 months
 - 4.2.5.3** Acute bacterial or fungal infection requiring intravenous antibiotics at the time of registration
 - 4.2.5.4** Chronic Obstructive Pulmonary Disease exacerbation or other respiratory illness requiring hospitalization or precluding study therapy at the time of registration
 - 4.2.5.5** Hepatic insufficiency resulting in clinical jaundice and/or coagulation defects; Note, however, coagulation parameters are not required for entry into this protocol.
 - 4.2.5.6** Pre-existing \geq grade 2 neuropathy
 - 4.2.5.7** Prior organ transplant
 - 4.2.5.8** Systemic lupus
 - 4.2.5.9** Psoriatic arthritis.
- 4.2.6** Known HIV positive.
HIV positive patients are known to have worse clinical outcomes especially for local, regional, and distant cancer control. This poorer prognosis is thought to be secondary to a compromised immune system. Thus, de-escalation of radiation and chemotherapy is not justifiable.
- 4.2.7** Current active smoker, defined as active cigarette smoking within the 6 months prior to enrollment.

5.0 STUDY PLAN

5.1 Schema

[figure not shown]

Figure 2: Schema

Figure 2: The primary objective of this study is to assess the 2 year PFS of HPV-associated OPSCC after genetic risk based de-intensified CRT. All patients with ≤ 10 pack years smoking history will receive de-intensified CRT. Patients with > 10 pack years smoking history, and select patients with extensive smokeless tobacco history (based on the PI's assessment), will have genetic assessment of their tumors (pre-treatment archival tissue or biopsies), and if p53 is mutated, they will receive an additional 10 Gy for a total radiation dose of 70 Gy (which is the historical, standard) and one additional weekly chemotherapy dose. Those with > 10 pack year smoking history and without the p53 mutation will receive the de-intensified regimen. Circulating free HPV DNA will be assessed pre-treatment, during treatment, and post-treatment at months 3, 6, 12, 18, and 24 (See Section 5.5 for details on blood collection time points).

5.2 Pretreatment Evaluations: All patients will have standard of care evaluation and staging procedures.

5.2.1 Complete history and physical exam including weight and performance status.

5.2.2 Completion of panendoscopy with directed biopsies and bilateral tonsillectomies if the primary is unknown is strongly recommended, but not required.

5.2.3 Completion of the following radiological studies:

at least contrasted neck CT and chest x-ray. Chest CT, PET/CT and/or MRI are optional studies. CT of the neck should have IV contrast unless contraindicated (allergy or adverse reaction or renal issues). PET/CT is satisfactory and can be done instead of or in addition to contrasted neck CT and chest x-ray. Pretreatment ultrasound evaluation with possible FNA is permissible to stage the neck prior to treatment.

5.2.4 Complete dental evaluation is recommended.

5.2.5 Completion of the following laboratory studies: CBC, serum chemistries, liver function tests, and pregnancy test if female.

5.3 HPV and/or p16 testing

HPV and/or p16 testing will be performed via fluorescence in-situ hybridization and immunohistochemistry, respectively. Methods and techniques for these tests have been established by the UNCH, UF, and Rex Cancer Center of Raleigh Departments of Pathology and these biomarkers are already routinely examined for all head and neck tumor specimens obtained at these institutions. This testing may be performed on FNA tissue obtained from a neck node. Results of HPV and/or P16 testing performed at institutions outside of the study site are acceptable.

5.4 Genetic Assessment

All patients with > 10 pack years smoking history, and select patients with extensive smokeless tobacco history (based on the PI's assessment), will have their tumor assessed (pre-treatment archival tissue/biopsy) for p53 mutational status. The UNC Molecular Genetics Laboratory will perform a mutation panel interrogating selected regions of 26 genes using next-generation sequencing (TruSight Tumor Panel®, Appendix). Genes assessed are listed in the appendix. The turn around time for these tests is approximately two weeks. Only p53 mutational status will be used to risk stratify. The other 25 analyzed genes (TruSight Tumor Panel®) will not be used to decide on whether a patient with > 10 pack years will receive de-intensified CRT. We will archive that data and analyze it retrospectively. Other participating centers will overnight ship tissue samples to UNC for genetic assessment as follows: Ten (10) unstained sections from formalin-fixed, paraffin-embedded tissue on plain, uncoated glass slides (4 microns thick); an H&E stained slide to allow pathologist documentation that sufficient tumor is present (if tissue exhibits less than 20% tumor, specimens are enriched for tumor by manual macrodissection to allow better assay sensitivity); and a copy of the surgical pathology report to assist in block selection, to document anatomic site, and to confirm histopathologic diagnosis of carcinoma. Alternatively, sites may send archival tissue in a formalin fixed paraffin embedded block (FFPE) in place of the slides.

We will be assessing a narrower number of genetic alterations in this proposal, as compared to the published/presented works of Dr. [REDACTED]. This decision was made out of necessity to ensure the feasibility (i.e., two week turn around time) of incorporating genomic information to prospectively guide treatment. Thus we are limited to evaluating a select number of genetic alterations, and are focusing the design of our study on p53 mutational status. Other mutational events may be useful in risk stratification, however we hypothesize that the central role of p53 in regulating the cell cycle and mitigating radiation and chemotherapy sensitivity make it the ideal biomarker to use in our proposal.

5.5 Circulating free HPV-DNA (cfHPV-DNA)

Previous versions of this protocol have detailed various requirements regarding blood specimen collection time points as the trial has evolved. These have included blood collection at pretreatment, weekly during treatment, and up to 5 post-treatment time points. As of May 8, 2020, blood specimens will only be collected at pre-treatment and Week 4 of treatment. One tube will be drawn at each time point. Circulating plasma DNA will be extracted and cfHPV-DNA will be quantified using our ddPCR assay using the Biorad QX-200 (████████ [name]'s lab). Additional exploratory analyses on plasma cfDNA samples may be performed in study co-investigator laboratories. Additional samples may be obtained at the PI's discretion. If necessary, each additional draw will be one Streck tube. UNC will provide Streck BCT tubes to other participating centers for blood collection. After sample is drawn, tube should be inverted 10 times to mix the preservative. Sites will overnight ship blood samples within one business day to UNC in FedEx boxes without ice for assessment (for samples collected on Friday, shipping on Monday is fine). If necessary for batch shipment, sites may wait to ship blood samples, but must ship within one week (5 business days) of the date the earliest sample was drawn.

Specimens will be retained indefinitely unless a specific participant chooses to withdraw from the study. Should a patient withdraw from this study, any specimens that have been collected, and that contain information that can be used to identify the participant will be destroyed. Any specimens that have been stripped of identifying information cannot be linked back to the participant, and therefore will not be destroyed.

Tissue and blood samples should be sent overnight (or by UNC courier) to ██████████ at the following address: Department of Radiation Oncology; UNC Cancer Hospital; [name]. Please notify ██████████ by phone ██████████ or email (██████████) when samples are shipped.

5.6 Radiation Therapy

All patients will receive Intensity Modulated Radiotherapy Treatments (IMRT) or proton radiotherapy. All patients will be initially planned to 60 Gy at 2 Gy/fx, 30 fx, once a day. The turn around time for genetic testing of pre-treatment tissue (archival or biopsy) is approximately two weeks. It is expected that during the first couple of weeks fo the initial 60 Gy plan that the genetic analysis will be completed for the patients with > 10 pack years. Should one of these patients have a p53 mutation an additional 2nd radiation plan ("boost plan") of 10 Gy at 2 Gy/fx will be done. Thus the total dose for patients with HPV-associated OPSCC, > 10 pack years, and p53 mutated will be 70 Gy, the standard dose (two radiatons plans, sequential boost).

5.6.1 CT simulation

CT simulation will be obtained with IV contrast for treatment planning purposes for all patients. For patients receiving proton therapy, a non-contrast CT simulation will also be performed. The head and neck area will be immobilized with an aquaplast mask. Patients will be positioned in the neck extended position.

5.6.2 Target and Organ at Risk Volumes:

5.6.2.1 Gross Tumor Volume (GTV): is defined as all known gross disease determined on the CT simulation scan.

5.6.2.2 High Risk Clinical Target Volumes (CTV-HR): is defined as the GTV plus a non-uniformly expanded 5 to 10 mm to account for high risk areas of microscopic spread. For situations where the primary tumor was removed with the biopsy (e.g. tonsillectomy) and the primary tumor cannot be seen on radiographic imaging the biopsy site will be included in the CTV-HR. For patients with an unknown primary (T0) the ipsilateral oropharynx (base of tongue, tonsil, soft palate) will be included in the CTV-HR volume.

5.6.2.3 Standard Risk Clinical Target Volume (CTV-SR): is defined as the elective nodal regions. The consensus guidelines for the node negative and node positive necks published by Gregoire et al. will be used as a guide to define the CTV-SR^{36,37}. For the situation of the unknown primary (i.e. T0), the nasopharynx will be included in the CTV-SR. The following guidelines will be used in delineating the CTV-SR.

5.6.2.3.1 *Node positive hemi-neck (ipsilateral or contralateral to the primary site)*³⁶: The following elective nodal regions should be included in the CTV-SR: Levels Ib-V and retropharyngeal. The cranial extent to the base of skull of Level II and retropharyngeal nodes should be electively irradiated.

5.6.2.3.2 *Ipsilateral node negative hemi-neck*³⁷: The following elective nodal regions should be included in the CTV-SR: Levels II –IV and retropharyngeal area. The cranial extent to the base of skull of Level II and retropharyngeal nodes should be electively irradiated.

5.6.2.3.3 *Contralateral node negative hemi-neck*³⁷: The contralateral parotid may be spared by omitting irradiation of the cranial portion of Level II and retropharyngeal region, defined as the Level II, retropharyngeal region above the transverse process of the C1 vertebrae and/or where the posterior belly of the digastric muscle crosses over the jugular vein. Contralateral neck irradiation may be completely omitted for well lateralized tonsil cancers, defined as having no invasion of the base of tongue, and minimal invasion of the soft palate (i.e. > 1 cm from the uvula)³⁸.

5.6.2.3.4 *Unknown Primary*: The above elective nodal irradiation guidelines will be used. Furthermore the nasopharynx will be included in the CTV-SR.

5.6.2.4 Planning Target Volumes (PTV): To account for daily setup errors, the CTV-HR will be expanded uniformly by 3 mm to create a High Risk Planning Target Volume (PTV-HR). The CTV-SR will be expanded uniformly by 3 mm to create a Standard Risk Planning Target Volume (PTV-SR).

5.6.2.5 Organs at Risk (OAR): The following normal tissues will be segmented on CT simulation scan: spinal cord, brainstem, parotids, cochleae, and larynx.

5.6.2.6 Planning Risk Volumes (PRV): OAR(s) will be uniformly expanded 3mm to create individual Planning Risk Volumes (PRV).

Dose Specification: Dose painting IMRT, passive-scattered proton therapy, or intensity modulated proton radiotherapy (IMPT) will be used and all doses will be specified to the PTV. The PTV-HR and PTV-SR will be treated to the following respective total doses: 60 Gy and 50 Gy. The dose per fraction to the PTV-HR and PTV-SR will be 2 Gy per day and 1.67 Gy per day respectively for IMRT and IMPT. Because the passive scattered proton technique is not conducive to a dose-painting strategy, both the PTV-HR and PTV-SR will receive 2 Gy per day using a sequential boost. The total number of fractions will be 30. All fields will be treated once a day Monday through Friday. All patients will be initially planned to 60 Gy at 2 Gy/fx, 30 fx, once a day. The turn around time for genetic testing of pre-treatment tissue (archival or biopsy) is approximately two weeks. It is expected that during the first couple of weeks of the initial 60 Gy plan that the genetic analysis will be completed for the patients with > 10 pack years. Should one of these patients have a p53 mutation an additional 2nd radiation plan (“boost plan”) of 10 Gy at 2 Gy/fx will be made for the PTV-HR. Thus the total dose for patients with HPV-associated OPSCC, > 10 pack years, and p53 mutation will be 70 Gy (two radiaton plans, sequential boost).

5.6.3 IMRT/Proton Treatment Planning

PTV's and PRV will be included in the radiotherapy optimization. Dose objectives will be chosen for the radiotherapy optimization based on previous institutional experience. Dose painting will be used to create one radiotherapy plan for IMRT and IMPT. The PTV-SR contours will encompass the PTV-HR contours. The dose to the PTV-SR plan will be 50 Gy at 1.67 Gy per daily fraction in 30 fractions. The PTV-HR will be treated to 60 Gy at 2 Gy per daily fraction in 30 fractions. For passive-scattered proton plans, a sequential boost technique will be allowed, and the dose to the PTV-SR will be 50 Gy at 2 Gy per daily fraction, and the PTV-HR will receive an additional 10 Gy (cumulative dose: 60 Gy) at 2 Gy per daily fraction. For those patients requiring a boost plan, the PTV-HR will receive an additional 10 Gy at 2 Gy per daily fraction in 10 fractions. IMRT/Proton radiotherapy to treat the entire neck is preferred, however a matched low anterior neck field photon technique may be used only if it does not result in significant dose heterogeneity for the PTV-HR. Proton therapy will be specified in Gy(RBE) (photon equivalents) to account for the inherent radiobiological differences between proton and photon therapies; thus, the treatments should be considered biologically equivalent.

5.6.4 Dose Constraints:

These apply to both patients who receive a total dose of 60 Gy or 70 Gy.

- PTV-HR and PTV-SR
 - 100% of the prescription should cover 95% of the PTV
 - No more than 1% of the PTV should receive $\geq 110\%$ of the prescribed dose

- No more than 1% of the PTV should receive $\leq 93\%$ of the prescribed dose
- Non-target Tissue
 - No more than 1% of the tissue outside the PTV should receive $\geq 110\%$ of the prescribed dose
- PRV
 - Spinal Cord: $0.1\text{cc} \leq 50\text{ Gy}$
 - Brainstem: $0.1\text{cc} \leq 54\text{ Gy}$
 - Parotid: Mean dose $< 26\text{ Gy}$ and/or $50\% < 30\text{ Gy}$
 - Cochlea: Mean dose $< 45\text{ Gy}$
 - Larynx: Mean dose $< 41\text{ Gy}$ and/or $60\text{ Gy} \text{ to } < 20\%$

PTV coverage should not be compromised to meet the dose constraints of the parotid, cochlea, or larynx. Sparing of these structures is left at the discretion of the treating radiation oncologists. The dose constraints for the spinal cord and brainstem must be satisfied. This may be done at the cost of altering the PTV.

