1.2 Standard of care CRT for OPSCC

The standard treatment regimen for HPV-associated oropharyngeal or unknown primary squamous cell carcinoma of the head and neck is 70 Gy, 2 Gy per day, 35 fractions, over 7 weeks with 2 to 3 doses of cisplatin 100mg/m². Most institutions perform a PET/CT at 10 to 16 weeks after CRT to assess response. Depending on the clinical response, patients may have to have a biopsy of the primary site and/or a neck dissection after treatment. Typically patients with a negative PET/CT scan are observed (i.e. no surgery). Standard CRT is associated with significant acute toxicity with most patients experiencing grade 3 and 4 acute toxicity during treatment. Furthermore, approximately 20% of patients will have Grade 3-4 long-term morbidity related to their definitive CRT.

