5.7 Chemotherapy

In our initial study, LCCC 1120, all patients were started on a regimen of cisplatin $30\text{mg}/\text{m}^2$ given intravenously over 60 minutes weekly during IMRT; 6 total doses for a total of $180\text{ mg}/\text{m}^2$. However, if cisplatin was not tolerated, it was permissible to switch to alternative, acceptable weekly chemotherapy regimens such as cetuximab, carboplatin, or carboplatin/taxol. For the proposed study, cisplatin is the preferred mandated first choice chemotherapy, however alternative weekly regimens are permissible. Typical reasons for a patient not being able to receive cisplatin include renal insufficiency and history of hearing loss. Justification for not using cisplatin must be documented.

Analysis of a prospective national registry, Longitudinal Oncology Registry of Head and Neck Carcinoma (LORHAN), showed that the three most commonly prescribed concurrent (with radiation) regimens (in order) are single agent cisplatin (51%), single-agent cetuximab (21%), and carboplatin plus paclitaxel (7%). Single agent carboplatin was infrequently used (3%) [redacted] et al. Cancer 2011;117:1679–86.). The acceptable weekly chemotherapy regimens that may be used on this study are the following:

- Cisplatin 30 to $40\text{ mg}/\text{m}^2$ (preferred, first choice)
- Cetuximab $250\text{mg}/\text{m}^2$ (preferred, second choice)
- Carboplatin AUC 1.5 and paclitaxel $45\text{ mg}/\text{m}^2$ (preferred, third choice)
- Carboplatin AUC 3 (preferred, fourth choice)

Chemotherapy will be given intravenously weekly during radiotherapy. 6 total doses will be given. It is preferred that the doses be administered on days 1, 8, 15, 22, 29, and 36;

however, this is not mandatory. Patients with the p53 mutation will receive one additional weekly chemotherapy dose. *Chemotherapy will not be given to patients with T0-2 N0-1 disease, < 10 pack years smoking history. For patients with T0-2 N0-1 disease, >10 pack years smoking history, whether or not the patient receives chemotherapy will be at the discretion of the treating physician.*

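### Section 5.6.3 gives the 10 Gy boost at 2 Gy per fraction as 10 fractions; it should be 5, for 70 Gy in 35 fractions

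*Combined protocol and SAP*

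**What the plan says.** All patients start on a plan of 60 Gy to the high-risk target volume (PTV-HR) in 30 once-daily fractions of 2 Gy (sections 5.6 and 5.6.3). Those whose tumour proves to carry a p53 mutation then have a sequential boost. The treatment-planning section, 5.6.3, prescribes it: "the PTV-HR will receive an additional 10 Gy at 2 Gy per daily fraction in 10 fractions".

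Other parts of the protocol describe the same boost:

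- Section 5.1 (Schema): "if p53 is mutated, they will receive an additional 10 Gy for a total radiation dose of 70 Gy".
- Section 5.6: a second plan of 10 Gy at 2 Gy per fraction, with the conclusion "Thus the total dose for patients with HPV-associated OPSCC, > 10 pack years, and p53 mutated will be 70 Gy, the standard dose".
- The Dose Specification paragraph under 5.6.2: again 10 Gy at 2 Gy per fraction, and "Thus the total dose for patients with HPV-associated OPSCC, > 10 pack years, and p53 mutation will be 70 Gy". The same paragraph sets the schedule: "All fields will be treated once a day Monday through Friday".
- Section 5.6.4, on the dose constraints: "These apply to both patients who receive a total dose of 60 Gy or 70 Gy".
- Section 5.7: "Patients with the p53 mutation will receive one additional weekly chemotherapy dose".

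Section 1.2 describes the standard regimen that the boosted course is meant to match: "70 Gy, 2 Gy per day, 35 fractions, over 7 weeks". Only 5.6.3 states a number of fractions for the boost.

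**The concern.** Dose, dose per fraction and number of fractions are tied together, so any two fix the third. In 5.6.3 the third does not follow from the other two, and a site cannot deliver the sentence as written. To honour the count of 10, it must break either the boost dose or the fraction size.

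This is a prescription in the operative text of a protocol with four named centres (section 1.1), and section 8.5 requires the study to be run as the protocol describes. The possible consequences are a longer course or a higher total dose than intended. Section 5.6.6 limits treatment breaks, so overall treatment time matters to this protocol. Section 6.2 says adverse events will not be reported, so a dosing discrepancy is less likely to surface by that route.

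**Working it through.** **Inputs**

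- Initial plan: 60 Gy, 2 Gy per fraction, 30 fractions (5.6, Dose Specification, 5.6.3).
- Boost: 10 Gy (5.1, 5.6, Dose Specification, 5.6.3) at 2 Gy per fraction (5.6, Dose Specification, 5.6.3), in 10 fractions (5.6.3 only).
- Schedule: one fraction a day, five days a week (Dose Specification).
- Standard course: 70 Gy, 35 fractions, 7 weeks (1.2).

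**Formula:** number of fractions = dose / dose per fraction.

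**The plan's other counts reproduce**

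- High-risk volume: 60 / 2 = 30 fractions, as stated.
- Standard-risk volume: 50 / 30 = 1.67 Gy per fraction, as stated.
- Passive-scattered protons: 50 / 2 + 10 / 2 = 25 + 5 = 30 fractions, the stated total. This step also adds 10 Gy at 2 Gy per fraction, and the total of 30 works only if that takes 5 fractions.

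**The boost count does not reproduce**

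- 10 / 2 = 5 fractions; the plan says 10.

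**What follows if the count of 10 is kept**

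| Held fixed | Boost | Full course | Conflicts with |
|---|---|---|---|
| 10 fractions and 2 Gy per fraction | 10 × 2 = 20 Gy | 60 + 20 = 80 Gy in 40 fractions | the 10 Gy boost and 70 Gy total in 5.1, 5.6 and Dose Specification |
| 10 fractions and 10 Gy | 10 / 10 = 1 Gy per fraction | 70 Gy in 40 fractions | the 2 Gy per fraction in 5.6, Dose Specification and 5.6.3 |

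Either way the course takes 40 / 5 = 8 weeks. An 80 Gy total would be 10 / 70 = 14% above the intended dose.

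**With the count set to 5**

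- Dose: 60 + 10 = 70 Gy.
- Fractions: 30 + 5 = 35.
- Duration: 35 / 5 = 7 weeks.

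All three agree with the standard course in 1.2.

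**Chemotherapy timing.** Six weekly doses on the preferred days 1 to 36, plus one more a week later, put the seventh on day 36 + 7 = 43. That is the first day of week 7 (6 × 7 + 1 = 43), which fits a seven-week course.

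**The case against.** The strongest reply is that the protocol corrects itself. The sentence at fault also carries the right dose and the right fraction size, 5.6 and Dose Specification give a boost prescription from which the count follows, and the 70 Gy total is stated repeatedly. A radiation oncologist or physicist writing the boost plan would probably notice the mismatch. No statistical quantity is touched and no misdosing is shown, so it could be called a minor slip. Section 8.4 also provides for annual auditing, although it does not mention fraction counts.

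Most of this is true, and it limits the seriousness of the point. It does not make the sentence deliverable, and the only boost fraction count in a multi-centre radiation protocol should be right.

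Two supporting arguments deserve less weight. Section 5.6.4 says which patients its constraints apply to; it does not itself restrict the permitted totals. The chemotherapy timing is only suggestive, because the preferred days are not mandatory and chemotherapy is discretionary for patients with T0-2 N0-1 disease and more than 10 pack years. The conclusion needs neither.

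Nothing suggests a text-extraction fault. The sentence is intact, the neighbouring figures are coherent, and it stands in the current body text, not in the amendment log.

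**Conclusion.** The error holds. The boost fraction count in 5.6.3 is 10 where it should be 5, twice the correct value. Taken with the 10 Gy dose it adds 5 treatment days, or one week. Taken with 2 Gy per fraction it also adds 10 Gy to the total.

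That the count is the number to change rests on the 10 Gy boost, the 2 Gy fraction and the 70 Gy total each being repeated elsewhere, while the count of 10 appears once and without support. The protocol does not itself write 35 fractions for the boosted group; that figure is 30 + 5, and it matches section 1.2.

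The point concerns only patients who receive the boost, and the documents do not give their number. The sample size, critical values, type I error, power and primary analysis are unaffected. It should be fixed because it is an operative prescription, but it is not a design flaw.

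**What to change.** In 5.6.3, change the boost count from 10 fractions to 5, and add that the boosted course totals 70 Gy in 35 fractions. The dose statements in 5.6 and Dose Specification need no edit.

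Check the delivered-dose records of all boosted patients against 70 Gy in 35 fractions, and report any departure. This is a precaution; the documents give no sign of misdosing.

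A separate, minor clarification could go into the same amendment. Section 5.1 assigns everyone with 10 or fewer pack years to the de-intensified regimen, but also provides the boost for selected smokeless-tobacco users whose tested tumour is p53-mutated. Sections 5.6 and Dose Specification mention only patients above 10 pack years, while 5.7 gives the extra chemotherapy dose with no pack-year limit. If the boost is meant for that group, one sentence in each of 5.1 and 5.6 would say so.

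The cost is one corrected number with a short statement of the total course, a records check limited to boosted patients, and two optional clarifying sentences.
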